## List of abbreviations

Abbreviation	Interpretation
100-mm VAS	100-millimeter visual analogue scale
BP	Blood pressure
ALT	Alanine aminotransferase
AST	Aspartate aminotransferase
APTT	Activated partial thromboplastin time
HIV	Human immunodeficiency virus
KOA	Knee osteoarthrosis
GGTP	Gamma-glutamyl transpeptidase
HA	Hyaluronic acid
CRO	Contract Research Organization
MD	Medical device
GCP	Good Clinical Practice
NSAID	Non-steroidal anti-inflammatory drugs
IEC	Independent Ethics Committee
AE	Adverse event
OA	Osteoarthrosis
PT	Prothrombin time
SAE	Serious adverse event
SOP	Standard operating procedure
ESR	Erythrocyte sedimentation rate
CRD	Chronic renal disease
RR	Respiration rate
HR	Heart rate
ALP	Alkaline phosphatase
eCRF	Electronic Case Report Form
ACR	American College of Rheumatology
JSW	Joint space width
WOMAC	Index of Western Ontario and McMaster Universities Osteoarthritis

[figure not shown]
#### 1.1 General provision

#### 1.1.1 Justification of selection of the clinical study type

The study design including the selection of the study population, endpoints, is developed in accordance with the recommendations laid down in the Guidelines of EMA on clinical investigations of products intended for osteoarthritis treatment [1], on products intended for symptom-modifying therapy of osteoarthritis (osteoarthrosis): multicenter randomized double-blind placebo-controlled, in parallel groups study.

The study is double-blind - a patient, study investigator and Sponsor representative (monitoring specialist) will not know to which group a patient is included.

#### 1.1.1.1 Study flow chart

#### 1.1.2 Measures aimed to minimize subjectivity

Due to various viscosity (which leads to different exertion in intra-articular injection) and different appearance of the study MD an placebo, to preserve blinding of any patient and study team, an independent unblended physician is to be engaged, he/she will receive the product per randomization code and perform the procedure of intra-articular injection of the study MD and placebo.

Randomization – a measure aimed to minimize subjectivity of patient random allocation. Randomization will exclude subjective, as well non-informed, selection of patient population to one of the group which will differ significantly from the population enrolled to the second one.

Placebo-controlled study – investigator and patient blinding will be used, via administration of the MD and comparator intervention depending on randomization results.

Patients will be randomized to groups using the simple block randomization method.

## 2 Description of statistical methods

### 2.1 Description of statistical methods to be used

Statistical analysis will be carried out using specialized software, the selection of which will be carried out during the preparation of the statistical analysis plan.

Continuous (quantitative) data will be presented using the number of observations, arithmetic mean, 95% confidence interval (CI) for mean, standard (mean-square) deviation, median, interquartile range (25th and 75th centile), minimum and maximum.

Qualitative data (ordinal, nominal) will be presented using absolute frequencies (number of observations), relative frequencies (percent) and 95% CI.

Unless otherwise specified in the statistical analysis plan, statistical tests will be two-sided with a 5% confidence level.

The medical history and AEs will be encoded using the MedDRA classifier in the current version. Concomitant and prior therapy will be encoded using the ATX classifier.

This section briefly describes the planned analysis. The full analysis will be described in the statistical analysis plan.

#### 2.1.1 Demographic data, baseline data and follow-up data

Demographic, baseline and follow-up characteristics, such as medical history (MedDRA classified) and co-medication will be described by treatment groups for the population depending on the initial treatment (intention-to-treat, ITT) and then safety, if they differ.

#### 2.1.2 Analysis of the primary efficacy parameter

In this study, the primary endpoint of effectiveness is selected to **total index score WOMAC** (WOMAC-T) against the use of medical device NOLTREX TM in comparison with placebo (0.9% sodium chloride solution).

The null hypothesis ( $H_0$ ) in this study is that the average change in the total WOMAC score (WOMAC-T) at visit 5 (week 25) compared to the basal value at visit 1 (week 1) will be equal in all groups.

An alternative hypothesis ( $H_A$ ) in this study is that the average change in the total WOMAC score (WOMAC-T) at visit 5 (week 25) compared to the basal value at visit 1 (week 1) will differ in at least one of the groups.

The analysis of the primary efficacy parameter will be carried out using covariance analysis (ANCOVA) (adjusted for the original WOMAC-T score). The factors will be the fixed factors of the treatment group and the radiological stage.

For pairwise comparison of groups of active medical device with placebo groups (for each stage of OA), after the covariance analysis, Tukey's HSD (honest significant difference) significance level

correction will be used, while 95% confidence intervals for corrected average changes will also be calculated (least square means).

The analysis of the primary efficacy parameter will be carried out both on the ITT population (main analysis) and on the PP population (additional analysis).

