$\label{lem:clinical} Clinical Study Protocol IA/PAAG-SI/OA/2019 \\ HBISA Endoprosthesis of synovial fluid NOLTREX^{TM}$

Multicenter, Double-blind, Randomized, Placebo-controlled Comparative Study of Efficacy and Safety of Intra-articular Polyacrylamide Hydrogel with Silver Ions (NOLTREX™) in patients with Knee Osteoarthritis K-L grades II-III

ClinicalTrials.gov Identifier: NCT03897686

Version 3.0: October 30, 2020

Study sponsor
"RC "BIOFORM" LLC
[name]
[name]

List of abbreviations

Abbreviation	Interpretation
100-mm VAS	100-millimeter visual analogue scale
BP	Blood pressure
ALT	Alanine aminotransferase
AST	Aspartate aminotransferase
APTT	Activated partial thromboplastin time
HIV	Human immunodeficiency virus
KOA	Knee osteoarthrosis
GGTP	Gamma-glutamyl transpeptidase
HA	Hyaluronic acid
CRO	Contract Research Organization
MD	Medical device
GCP	Good Clinical Practice
NSAID	Non-steroidal anti-inflammatory drugs
IEC	Independent Ethics Committee
AE	Adverse event
OA	Osteoarthrosis
PT	Prothrombin time
SAE	Serious adverse event
SOP	Standard operating procedure
ESR	Erythrocyte sedimentation rate
CRD	Chronic renal disease
RR	Respiration rate
HR	Heart rate
ALP	Alkaline phosphatase
eCRF	Electronic Case Report Form
ACR	American College of Rheumatology
JSW	Joint space width
WOMAC	Index of Western Ontario and McMaster Universities Osteoarthritis

Synopsis

Study title	Multicenter Double-blind Randomized Placebo-controlled Comparative			
	Study of Efficacy and Safety of Intra-articular Polyacrylamide			
	Hydrogel with Silver Ions (NOLTREX TM) in patients with Knee			
	Osteoarthritis K-L grades II-III			
Protocol number	IA/PAAG-SI/OA/2019			
Study MD	HBISA Endoprosthesis of synovial fluid NOLTREX TM (4.0 ml for one			
	injection with one-week interval between injections. Course - 2 injections).			
Placebo	Sodium chloride solution 0.9% BUFUS®, in ampoules 10 ml (to be used			
	with syringes 2.5 ml). (4.0 ml for one injection with one-week interval			
	between injections. Course - 2 injections.)			
	ber Proposed total study period – 12 months.			
of study sites and patients	Participation of each patient in the study – not more than 179 days:			
	• Screening – days -70;			
	• Treatment period: weeks 1-2;			
	• Follow-up period: weeks 3-25.			
	Number of study sites – 4.			
	Number of patients:			
	- 170 screened patients;			
	- 144 randomizations (72 patients in each group);			

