- Change of stiffness (WOMAC-B) and functionality (WOMAC-C) subscale scores on Visit 3 (Week 6), Visit 4 (Week 13) and Visit 5 (Week 25) in comparison with baseline on Visit 1 (Week 1);
- Patient's assessment of the treatment efficacy, value OEP (per scale from 1 evident aggravation to 6 significant improvement) on Visits 5, 6 and 7 (values OEP-w₆, OEP-w₁₃, OEP-w₂₅);
- Investigator's assessment of the treatment efficacy, value OEI
 (per scale from 1 evident aggravation to 6 significant
 improvement) on Visits 3, 4 and 5 (values OEI-w₆, OEI-w₁₃, OEI-w₂₅);
- Assessment of the total number of paracetamol tablets taken (one tablet = 500 mg) beginning from day 1, on Visits 3, 4 and 5 (values PARACETAMOL-w₆, PARACETAMOL-w₁₃ and PARACETAMOL-w₂₅, correspondingly);

- Assessment of the total number of NSAID tablets taken starting from day1, on Visits 3, 5 and 5 (values NSAID-w₆, NSAID-w₁₃, NSAID-w₂₅ correspondingly);
- Patient exclusion rates due to safety (subject exclusion criteria 2, 3, 6, 7);
- Patient exclusion rates due to poor patient's treatment compliance (criteria 4 and 5).

Safety assessment parameters:

- Frequency of AE and/or SAE reporting in treatment groups;
- Global study physician and patient assessment of the therapy intolerability;
- Vital signs (HR, BP, body temperature, RR);
- Laboratory test results.

AE description will be presented per the following scheme:

- AE description;
- Severity of manifestation;
- Duration:
- Relationship with the study product;
- Outcome.

AE will be encoded in accordance with the Medical Dictionary for Regulatory Activities MedDRA.

Inclusion criteria

- 1) Men and women above 50 years;
- 2) Verified knee osteoarthritis in accordance with the ACR criteria (knee pain combined with one of the following signs: age above 50 years, knee crepitus or morning joint stiffness lasting for less than 30 minutes combined with radiologic signs of knee osteoarthritis);
- Kellgren Lawrence radiological grade II-III knee osteoarthritis with the predominant involvement of the medial tibiofemoral region of the knee joint;
- 4) Joint space width (JSW) of the target knee joint at least 2.5 mm.

Non-inclusion criteria

 History of any injury or surgical intervention on the target knee joint (except for diagnostic arthroscopy made more than 60 days before study entry);

- Severe degenerative changes in the target knee joint determined as the joint space narrowing less than 2 mm;

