# 2.3 Planned number of participants in a clinical trial with justification of sample size

The calculation of the sample size is based on the study results of the medical device NOLTREX TM for OA (osteoarthritis) of the knee joint (N. V. Zagorodny et al. The use of new biopolymer material Noltrex in the complex treatment of patients with gonarthrosis. 2012, t. 17, No. 6, p. 49-52)[3]. Application in this study during the first 10 days of NSAID Movalis does not affect the assessment of results after 13 and 25 weeks.

As the primary endpoint in the study the change in total score on the WOMAC scale in the affected joint (WOMAC total) was chosen, at Visit 7 (week 25) compared to the basal value at Visit 1 (week 1). The choice of "Week 25" assessment point is related to the fact that in the above study the effect of medical device NOLTREX TM was maximal after 6 months from the injection, and then the effect of the treatment was decreasing. An additional endpoint - a change in the total score on the WOMAC

scale (WOMAC total) at Visit 6 (week 13) compared to the basal value at Visit 1 (week 1) will be used to assess the onset of the effect of medical device after 3 months from the injection.

For the calculations the following assumptions were used:

- 1) Two groups (fixed factor A) medical device NOLTREXTM and placebo
- 2) Baseline of WOMAC level and the total dose of NSAIDs received in the duration of study as covariates
- 3) Effect size 0.25: calculated on the basis of data from the above publication, in which the magnitude of differences between groups, taking into account the variability, was up to 100 points, and the variability (standard deviation) up to 400 points
- 4) Level of significance = 5% (type I error  $\alpha$  = 0.05)
- 5) Power 80% (type II error  $\beta$  = 0.20)
- 6) Statistical model covariance analysis (adjusted for the initial value) with fixed factors of the group
- 7) Drop-outs during the study will not exceed 10%.
- 8) Drop-out during inclusion period (screening) will not exceed 15%.

Calculations of the sample size (the number of completed cases) were performed using the G\*Power 3.1.9.2 software package with the above assumptions:

F tests - ANCOVA: Fixed effects, main effects and interactions

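### The primary ANCOVA of a 4-site trial leaves study site out of the model; adding it is a cheap, modest gain in efficiency and clarity

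*SAP*

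**What the plan says.** The protocol synopsis sets the scale: "Number of study sites – 4". SAP 2.1.2 has the primary analysis "carried out using covariance analysis (ANCOVA) (adjusted for the original WOMAC-T score"), and then: "The factors will be the fixed factors of the treatment group and the radiological stage". Site is not a term. SAP 2.1.3 gives the quantitative secondary endpoints a similar analysis, so they inherit the omission; the frequency endpoints use a chi-square test.

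On allocation, SAP 1.1.2 says only: "Patients will be randomized to groups using the simple block randomization method". The protocol synopsis says the same. Neither names a stratification factor or says whether blocks run within site or centrally. SAP 3.1 mentions a randomisation plan and table, which are not part of the documents supplied.

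The sample size in SAP 2.3 assumes two covariates, baseline WOMAC and total NSAID dose. Site is not among them.

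**The concern.** WOMAC is completed by patients and the global efficacy rating partly by investigators, so scores may plausibly differ between sites after adjustment for baseline. Site is known for every patient. Leaving it out puts whatever it explains into the residual and widens the confidence interval for the treatment effect.

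A second consequence depends on how the block list was built. If blocks run within site, the arms are balanced by site and the true variance of the treatment estimate is smaller than the one a model without site reports. The test then rejects too rarely under the null. If blocks do not run within site, chance imbalance between sites is controlled neither in the design nor in the model. In both cases the reader cannot tell from the SAP whether the model matches the randomisation.

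**Working it through.** **Inputs.** From SAP 2.3: f = 0.25, alpha 0.05, 130 completers at 1:1. From SAP 2.1: "statistical tests will be two-sided with a 5% confidence level". From the synopsis: 4 sites, hence 3 df. The share r of residual variance due to site is not in the documents; it is an assumption, shown from 0 to 10%.

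**1. The plan's own figure.** λ = N·f²; denominator df = N − groups − covariates. At N = 128: λ = 128 × 0.0625 = 8.000, df = 128 − 2 − 2 = 124, critical F = 3.91755, power = 0.80136. These match the printed output; the printed total of 130 fits the rounding that the SAP mentions. At N = 130: λ = 8.125, df = 126, power = 0.807. The model in SAP 2.1.2 (treatment, grade, baseline) also leaves 126 df, so 0.807 is the reference.

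**2. Adding site.** The residual variance falls by the factor (1 − r) and df becomes 123. With arms balanced by site, λ = 8.125/(1 − r). Without that balance, chance imbalance inflates the variance of the treatment estimate on average by 1 + 3/129 = 1.023, so λ = 8.125/[(1 − r) × 1.023].

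| r (assumed) | λ, balanced | power | λ, not balanced | power |
|---|---|---|---|---|
| 0% | 8.125 | 0.807 | 7.940 | 0.798 |
| 2% | 8.291 | 0.815 | 8.102 | 0.806 |
| 3% | 8.376 | 0.819 | 8.186 | 0.810 |
| 5% | 8.553 | 0.827 | 8.358 | 0.818 |
| 10% | 9.028 | 0.846 | 8.823 | 0.838 |

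Against 0.807, the change at 5% is +1.1 (not balanced) to +2.0 points (balanced), and at 10% +3.1 to +3.9. Without balance the break-even lies between r = 2% (0.8063) and 2.5% (0.8082), against 0.8075 now. The largest loss, at r = 0, is 0.9 points.

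**3. Blocks within site, site left out.** The true variance of the estimate is (1 − r) times what the model uses, so the null is rejected only when a correctly scaled t exceeds 1.979/√(1 − r).
- r = 5%: 1.979/0.975 = 2.030, type I error 4.4%.
- r = 10%: 1.979/0.949 = 2.086, type I error 3.9%. A simulation of 4,000 trials gave 3.7%.

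Under such blocking the present model's power is 1 − T(1.979/√(1 − r)), with T the noncentral t distribution with 126 df and noncentrality √(8.125/(1 − r)). That gives 0.8135 at 5% and 0.8199 at 10%. The gain from the model change alone is then 0.8268 − 0.8135 = 1.3 points and 0.8464 − 0.8199 = 2.65 points.

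**4. Unstratified allocation, site left out.** Simulation (4,000 trials per scenario, r from 0 to 10%, 3% of variance from K-L grade assumed) gave a type I error of 4.9 to 5.3%. The test is valid.

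**The case against.** The best defence is that the gain is uncertain. The documents give no site variance. Baseline WOMAC-T is already a covariate and absorbs much of any difference in severity between sites. If little is left and arms are not balanced by site, adding site costs slightly more than it returns. All of this stands, and it is why the gain is given as a range that includes a small loss.

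The power reference is also open to question. The inputs in SAP 2.3, 100 points over an SD of 400, give a standardised difference of 0.25, which for two equal groups is f = 0.125. Power at 130 is then about 29%, and site at r = 5% brings it to about 30 to 31%. The direction is the same, but the gain is smaller in absolute terms, and the sample-size question is much larger than this one.

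A reader might infer three stronger points that the documents do not support.
- **Precision is being given away for free.** It is not free: it costs 3 df and depends on an unknown site share.
- **The list should be stratified by K-L grade**, because SAP 2.1.2 also plans comparisons by grade ("For pairwise comparison of groups of active medical device with placebo groups (for each stage of OA")). Grade is already a model factor, so its prognostic variance is removed either way. In 20,000 simulated allocations of 65 per arm, the mean variance inflation from chance grade imbalance was about 0.8%, or 130 × 0.008 ≈ 1 patient. The documents do not give the split between grades, so no firm figure for the within-grade comparisons is available.
- **Randomisation is unstratified.** The documents are silent on strata. They do not say there are none, and the randomisation plan may specify them.

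**Conclusion.** The point holds as a minor one about efficiency and clarity. Site is missing from the stated primary model and from the quantitative secondary models of a 4-site trial, without a reason. At N = 130 and f = 0.25, including it is worth about 1 to 2 points of power at an assumed site share of 5% and 3 to 4 points at 10%, measured against 0.807. Below about 2 to 2.5% without balance by site, it costs less than 1 point. If blocks run within site, the present test is slightly conservative (about 4.4% at a 5% share, 3.9% at 10%), not inflated.

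A reader might infer that the primary test is invalid. It is not: under unstratified allocation its type I error stays near 5%, and under blocks within site it errs on the safe side.

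**What to change.** In SAP 2.1.2, and through it in 2.1.3 for the quantitative endpoints:
- add study site (4 levels) as a fixed factor beside treatment, K-L grade and baseline WOMAC (baseline WOMAC-T for the primary endpoint);
- pre-specify a rule for pooling very small sites, based on numbers enrolled and not on outcome;
- state in SAP 1.1.2 whether blocks run within site or by any other factor, and include every such factor in the model.

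No change to the randomisation list is needed. The chi-square analyses in SAP 2.1.3 are untouched.

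**Cost.** 3 degrees of freedom and, in the unfavourable case above, under 1 point of power. SAP 2.7 lets the sponsor change the statistical plan, with the justification reported in the final study report. SAP section 4 does not treat a protocol amendment that affects statistical methods as minor, so the approval route should be checked. The change should be fixed before unblinding, so that the choice of model cannot depend on the results.

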#### 2.1.3 Analysis of secondary efficacy parameters

An analysis of the following secondary efficacy parameters is planned:

- Changing the overall score on the WOMAC scale (WOMAC-T) on Visit 4 (week 13) compared to the basal value on Visit 1 (week 1);
- The change in score on the subscale of pain (WOMAC-A) on Visit 3 (week 6), Visit 4 (week 13) and Visit 5 (week 25) and compared with the basal value on Visit 1 (week 1);
- The change in the score for the stiffness (WOMAC-B) and functionality (WOMAC-C) on Visit 3 (week 6), Visit 4 (week 13) and Visit 5 (week 25) compared to the basal value on Visit 1 (week 1);
- Evaluation of the treatment efficacy by the patient, the value OEP (on a scale of 1 a clear deterioration to 6 a significant improvement) at visits 3, 4 and 5 (OEP-w6, OEP-w13, OEP-w25);
- Evaluation of the effectiveness of treatment by the investigator, the value OEI (on a scale of 1 a clear deterioration to 6 a significant improvement) on visits 3, 4 and 5 (indicators OEI-w6, OEI-w13, OEI-w25);
- Assessment as per patient diary of the total number of paracetamol tablets taken (one tablet = 500 mg) starting on day 1, on visits 3, 4 and 5 (PARACETAMOL-w6, PARACETAMOL-w13 and PARACETAMOL-w25, respectively);
- Assessment per patient diary of the total number of NSAID tablets, starting on day 1, at visits 3, 4, 5 (values NSAID-w6, NSAID-w13 and NSAID-w25, respectively)
- Drop-out rate due to safety (exclusion criteria 2, 3, 6, 7);
- Drop-out rate due to low patient adherence to treatment (criteria 4 and 5).

For secondary efficacy parameters, the following statistical analysis methods are planned:

- For quantitative indicators, an analysis similar to the analysis of the primary endpoint (covariance analysis) followed by the identification of groups with significant differences using Tukey's HSD.
- For frequency indicators (segments) comparison of groups using the  $\chi^2$  criterion ("chi-square").

Analysis of secondary efficacy parameters will be conducted on the ITT population (main analysis) and on the PP population (additional analysis).

